#### 6.8.3 Important Risks

Summarized overall and by age cohort. All standard MedDRA queries (SMQs based on MedDRA version 17.1) listed below will include broad and narrow terms unless noted.

- Nephrotoxicity:
  - o Acute renal failure SMQ
  - o HLT Glomerulonephritis and nephrotic syndrome
  - o HLT Nephritis NEC
  - o HLT Nephropathies and tubular disorder NEC
  - o PT Hematuria (10018867)
- Hypersensitivity
  - o Hypersensitivity SMQ
  - o HLT Immune response protein analyses NEC
- Infusion related reaction: events occurring within 24 hours of infusion or the next calendar day if the time (AE onset or start of infusion) is missing. Medical adjudication will be performed to determine whether the event is a possible infusion related reaction.
- Hypersensitivity excluding medically reviewed infusion related reaction: Hypersensitivity SMQ events minus events adjudicated as possible IRRs.

An overall summary of adverse events of important risks include total number of events, number of SAEs, number of treatment-related events, number of unrelated events, number of mild events, number of moderate events, number of severe events, and number of events occurring on the same day as an infusion.

A corresponding listing will be generated for each table of AE of important risks. If applicable, a table corresponding to the adverse events of important risks that were related to study drug and/or moderate or severe will be produced.

#### 6.8.4 Risks Associated with Other Antisense Oligonucleotides

All standard MedDRA queries (SMQs based on MedDRA version 17.1) listed below will include broad and narrow terms unless noted.

- Hepatotoxicity:
  - o Hepatic failure SMQ
  - o Fibrosis and cirrhosis and other liver damage-related conditions SMQ
  - o Hepatitis, non-infectious SMQ
  - o Cholestasis and jaundice of hepatic origin SMQ
  - o Liver related investigations, signs and symptoms SMQ
  - o Liver-related coagulation and bleeding disturbances SMQ
- Thrombocytopenia: Hematopoietic thrombocytopenia SMQ

An overall summary of adverse events of risks associated with other antisense oligonucleotides include total number of events, number of SAEs, number of treatmentrelated events, number of unrelated events, number of mild events, number of moderate events, number of severe events, and number of events occurring on the same day as an infusion.

A corresponding listing will be generated for each of AE of risks associated with other antisense oligonucleotides.

#### 6.8.5 Risks Associated with the Studied Population

All standard MedDRA queries (SMQs based on MedDRA version 17.1) listed below will include broad and narrow terms unless noted.

- Serious blood stream infections with implantable venous access device (IVAD):
  - o Sepsis SMQ (available in MedDRA V22.1)
  - o Toxic septic shock conditions SMQ Narrow
  - o PT Vascular device infection
  - o PT Bacteraemia, Viremia, Fungemia, Sepsis, or Septic shock
  - o HLT Implant and catheter site reactions
  - o HLGT Device issues

- o Verbatim terms containing "port", "central venous", and "central line"
- Rhabdomyolysis: Rhabdomyolysis/myopathy SMQ

An overall summary of adverse events of risks associated with the studied population include total number of events, number of SAEs, number of treatment-related events, number of unrelated events, number of mild events, number of moderate events, number of severe events, and number of events occurring on the same day as an infusion.

#### 6.8.7 Vital Signs

Vital signs will be summarized overall and by age cohort using descriptive statistics. For each vital sign, the Baseline and final observations (within 28 days of the last dose of eteplirsen) will be presented overall and by age cohort. Additionally, the largest absolute change from Baseline will be summarized. Descriptive statistics will be calculated for the observed values as well as the change from Baseline values.

A table of treatment-emergent markedly abnormal results of vital signs that occur after Baseline as defined in Appendix Table 4 will be generated overall and by age cohort. The number and percentage of patients experiencing the abnormality as well as the total number of abnormalities will be presented. All vital sign values with an abnormality of interest will be listed.

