- b Patients not previously genotyped may beconsented and havegenotypeperformed as part of the study. Oncethe genotype is con firmed, all additional screening procedures will be performed -2 weeks from Week 1/Baseline. Patients may be enrolled in the study based on historical DNA test results; however, a blood sample for DNA testing will be obtained on all patients to confirm DMD mutation(s). In addition, a second blood sample will be obtained for genotyping of LTBP4 and SPP-1. So that total blood volume taken for the Screening visit does not exceed recommendations, theblood sample for DMD genotyping may be drawn at any time prior to the Week 2 visit and theblood sample for LTBP4 and SPP-1 may be drawn at any timeduring the dose-titration period. If the confirmatory DNA sample is negative for DMD on any enrolled patient, that patient will be withdrawn from the study.
- ^c Clinical safety laboratory assessments (blood chemistry [including liver function], renal function, hematology [including pla telets], and coagulation) must be obtained with results available within 2 weeks prior to dosing. (See Section 10.3.5 for the list of tests to be completed.)
- ^d Pla sma PK samples will be collected pre-dose, immediately prior to the end of infusion (prior to flush) and approximately 1-3 hours and 6-8 hours after completion of study drug infusion. Urine PK will be collected over the first 4 hours after start of infusion.
- ^c Vital signs include blood pressure, heart rate, respiration, and temperature. On infusion days, vital signs will be measured within 60 minutes prior to infusion, within 5 minutes (±2) after the end of infusion, and at 30 minutes (±5), and 60 minutes (±10) after the end of the infusion. All assessments will be performed after patients have remained calm for 5 minutes. Pulse rate and respiratory rate should be measured over 1 minute.
- ^f Weight will be measured prior to study drug infusions at thespecified visits.
- ^g Height/length will be measured as part of every physical examination. The examination will include general appearance; head, ears, eyes, nose, and throat; heart; lungs; chest; abdomen; skin; lymph nodes; musculoskeletal; and neurological systems.
- A 2-week window is allowed in the event the child is unable to complete this assessment at a given visit.
- Only performed in patients 36 months of age and older

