7.3. Study Endpoints

7.3.1. Primary Endpoint

The primary endpoint is safety and tolerability of eteplirsen in this study population, as measured by:

- Incidence of AEs
- Abnormal changes from Baseline or clinically significant worsening of clinical safety laboratory abnormalities (hematology, chemistry, coagulation, urinalysis)
- Abnormal changes from Baseline or worsening of vital signs
- Abnormal changes from Baseline or worsening of physical examination findings
- Abnormal changes from Baseline or clinically significant worsening of ECGs and ECHOs

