#### 8.1.4 Appendix Table 4. Vital Sign Abnormalities of Interest

Variable	Units	Markedly Abnormal Criteria Lower limit	Markedly Abnormal Criteria Upper limit
Systolic blood pressure	mmHg	< 90	> 140
Diastolic blood pressure	mmHg	< 40	> 90
Pulse Rate	beats/minute	< 60	> 130
Respiratory Rate	Breaths/min	< 12	> 20
Temperature	°C	< 36.0	> 38.0
Weight	kg	Decrease of 7% or more from Baseline	

Variable	Units	LLN	ULN	Age Group (years)	Markedly Abnormal Criteria
Heart Rate	beats/min	60	130		NA
QTcF Interval	msec	NA	NA	< 12	> 480
				All	< 320
					Increase > 60
					> 450
					> 480
					> 500
QRS Interval	msec	NA	NA	< 12	Intraventricular conduction delay (IVCD) or any QRS conduction disturbance with a QRS > 110 msec
PR Interval	msec	NA	NA	< 12	> 190
LVEF	%	NA	NA	All	< 55%
Fractional Shortening	%	NA	NA	All	< 29%

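### SAP Appendix Table 4 flags vital signs in children aged 6 to 48 months by fixed limits with no age band and, weight apart, no change-from-Baseline condition, so the respiratory-rate row is probably uninformative

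*SAP*

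**What the plan says.** The primary endpoint (Protocol 7.3.1, repeated in SAP section 3) includes "Abnormal changes from Baseline or worsening of vital signs". For this component, Protocol 13.8.2.2 plans frequency tables of predefined change to abnormal. The SAP's version is in 6.8.7: "A table of treatment-emergent markedly abnormal results of vital signs that occur after Baseline as defined in Appendix Table 4 will be generated". This is done for each cohort and for both combined. It reports how many patients, and what percentage, have the abnormality, together with the total count of abnormalities.

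The limits in Appendix Table 4 (SAP 8.1.4) include:

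- "Systolic blood pressure mmHg < 90 > 140"
- "Pulse Rate beats/minute < 60 > 130"
- "Respiratory Rate Breaths/min < 12 > 20"

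The table has no age column. Only the weight row refers to Baseline: "Decrease of 7% or more from Baseline".

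SAP 5.7 treats an abnormality as treatment-emergent if it occurs or worsens after dosing starts and within 28 days of the last dose. It does not say how much worsening is needed. Besides the pre-infusion reading, the Protocol section 2 footnote to Table 2 requires readings "within 5 minutes (±2) after the end of infusion, and at 30 minutes (±5), and 60 minutes (±10) after the end of the infusion". SAP 7.1 declares one change from the protocol, the removal of the interim analysis, and says there are no others.

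**The concern.** Every child is 6 to 48 months old at entry, yet one set of limits serves all of them and no source or reason for the limits is given. The component to be measured is change from Baseline or worsening, but the blood pressure, pulse and respiratory-rate rows test only whether a value lies beyond a fixed line. If usual values at these ages lie near or beyond that line, the row describes age and not the drug.

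Elsewhere the SAP uses the ideas missing here. Appendix Table 1 has predefined-change columns and criteria relative to Baseline. Section 6.8.9 drops physical examination findings that show no change from Baseline. Appendix Table 5 shows heart rate 60 and 130 only as lower and upper limits of normal, with no markedly abnormal criterion, whereas Appendix Table 4 calls the same values for pulse markedly abnormal.

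At stake is the only planned vital-sign summary that classifies values as abnormal, in an uncontrolled study whose primary endpoint is safety.

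**Working it through.** The plan states no expected flag rate, so there is no figure to reproduce.

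**1. Readings per child.** There are four readings per weekly infusion (Protocol section 2). The Week 1 pre-infusion reading is taken as Baseline (Protocol 13.1: last value before dosing).

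- Week 12: 12 × 4 − 1 = 47
- Week 48: 48 × 4 − 1 = 191
- Week 96: 96 × 4 − 1 = 383, or 191 + 48 × 2 = 287 if readings fall to two per visit after Week 48 (Protocol 10.3.2)

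**2. Effect of counting any single reading.** With independent readings and per-reading probability p, P(ever flagged) = 1 − (1 − p)^n. At n = 191, p = 1.2% already flags 90% of children.

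**3. Per-reading probability.** The means and SDs below are assumptions, because the documents give no norms. Normal tail areas use a half-unit continuity correction.

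- Respiratory rate > 20, as 1 − Φ((20.5 − mean)/SD): mean 20 gives 43% (SD 3) and 46% (SD 5); mean 22 gives 69% and 62%; mean 30 gives 99.9% and 97%.
- Systolic < 90, as Φ((89.5 − mean)/SD): mean 90 gives 48% (SD 8 or 10); mean 100 gives 9.5% (SD 8) and 15% (SD 10).
- Pulse > 130, as 1 − Φ((130.5 − mean)/12): mean 110 gives 4.4%; mean 130 gives 48%.

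**4. Ever flagged, allowing for correlation within a child.** Beta-binomial: P = 1 − B(a, b + n)/B(a, b), with a = p(1 − ρ)/ρ and b = (1 − p)(1 − ρ)/ρ. Here ρ is assumed to be 0.1 / 0.3 / 0.5, and any post-Baseline reading beyond the limit counts.

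| Limit and assumed mean | p | n = 47, independent | n = 47, ρ = 0.1 / 0.3 / 0.5 | n = 191, ρ = 0.1 / 0.3 / 0.5 |
|---|---|---|---|---|
| Respiratory rate, 22 (SD 3) | 0.69 | 100% | 100 / 99.8 / 97.6% | 100 / 100 / 99.1% |
| Respiratory rate, 20 (SD 3) | 0.434 | 100% | 100 / 97.4 / 88.1% | 100 / 99.4 / 93.5% |
| Systolic, 90, or pulse, 130 | 0.48 | 100% | 100 / 98.3 / 90.8% | 100 / 99.6 / 95.3% |
| Systolic, 100 (SD 8) | 0.095 | 99.1% | 80.6 / 52.2 / 34.9% | 93.5 / 64.8 / 43.0% |
| Pulse, 110 (SD 12) | 0.044 | 87.9% | 52.8 / 28.7 / 17.9% | 71.6 / 38.1 / 22.8% |

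**5. Two readings of worsening.** If any value worse than Baseline counts, and Baseline and later readings are exchangeable, a child already beyond the limit at Baseline is flagged with probability 191/192 = 99.5%. If only a normal-to-abnormal shift counts, that child can never be flagged. The simulation for respiratory rate uses n = 191, a between-child SD of 2 and a within-child SD of 2 (assumed).

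| Assumed mean | Beyond 20 at Baseline | Flagged, any worsening | Flagged, shift only |
|---|---|---|---|
| 18 | 19% | 91% | 73% |
| 20 | 43% | 98% | 56% |
| 24 | 89% | 99% | 11% |
| 28 | 99.6% | 99% | 0.4% |

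**6. Would age bands alone be enough?** Suppose age-banded limits cut off 2% of ordinary readings. Independent readings give 1 − 0.98^191 = 97.9% of children flagged; at ρ = 0.1 the figure is 43%. At 1% and 0.1% per reading, independence gives 85.3% and 17.4%. The ever-abnormal count can therefore stay high even with good limits. One weekly reading that must be abnormal in two consecutive weeks (47 pairs, treated as independent) gives 1 − (1 − 0.02²)^47 = 1.9%.

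**The case against.** - **No paediatric ranges in the documents.** This stands. That ordinary readings at these ages cross the limits is an assumption, and every size above depends on it.
- **Saturation is not general.** A reader might infer that all three rows approach 100% in both cohorts. The documents do not support that: they give no values by cohort, and the four readings around an infusion come from the same child. Correlation takes the low-end systolic and pulse figures well below saturation. Only the respiratory-rate row is robust, and only if typical values are near or above 20.
- **The data are not lost.** A reader might also infer that an infusion effect on vital signs could not be told from normal physiology. That goes too far. SAP 6.8.7 also gives observed values, change from Baseline, the largest absolute change and a listing of flagged values. Sections 6.8.2 and 6.8.3 analyse events within 24 hours of infusion, with medical adjudication in 6.8.3.
- **Appendix Table 5 is weak evidence.** Its band below 12 years contains every child at entry, so it does not show that the SAP distinguishes ages within this population.
- **Limited consequence.** The study has about 12 patients, safety is descriptive, no between-cohort test is planned, and the laboratory and hypersensitivity stopping rules in Protocol 10.3.4 do not use Appendix Table 4. This lowers the severity but does not answer the mismatch between the endpoint and the criteria.

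**Conclusion.** The concern holds as a defect of one summary table. From the documents alone: the limits are fixed, have no age band and, except for weight, are not tied to Baseline; the endpoint and the protocol's planned table both concern change; SAP 7.1 does not declare the departure; any single reading counts; and worsening is unquantified.

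The size rests on assumed values. At a mean respiratory rate of 20 to 30/min (SD 3 to 5), 43% to over 99% of single readings exceed 20. The row then flags nearly every child if any worsening counts. If only a shift counts, it nearly empties at the higher means, and at a mean of 20 it mostly records which side of the limit the Baseline reading fell on. In each case it says little about the drug. For systolic pressure the effect is conditional (assumed mean 90 to 100: 10% to 48% of readings). For pulse it is uncertain (assumed mean 110 to 130: 4% to 48%). Within-child correlation lowers the ever-flagged share for both.

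This should be fixed. It does not invalidate the vital-sign component of the primary endpoint.

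**What to change.** Amend the SAP before database lock, so that the criteria are not chosen after seeing the data:

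1. In Appendix Table 4, replace the single limits for blood pressure, pulse and respiratory rate with age-banded paediatric limits from a cited source, applied at the child's age on the day of the reading.
2. Require, in addition, a prespecified numerical change from Baseline or from that day's pre-infusion reading.
3. In SAP 5.7, define worsening numerically for vital signs, including how a child already beyond a limit at Baseline is handled.
4. Beside the ever-abnormal count, report the share of readings flagged, or abnormalities confirmed on a later reading. Step 6 of the working shows why age bands alone may not be enough.
5. Record the change in SAP 7.1.

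The cost is SAP wording and an age lookup in programming. Age and pre-infusion readings are already collected, so no new data are needed. One small downside is that the flags would not match any produced under the current limits in the sponsor's studies of older patients, so pooled tables would need the old flag as well.

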#### 6.8.8 Electrocardiograms and Echocardiograms

ECG and ECHO assessments will be summarized overall and by age cohort using descriptive statistics. For each ECG and ECHO parameter, the Baseline and final observations (within 28 days of the last dose of eteplirsen) will be presented overall and by age cohort. Additionally, the largest absolute change will be summarized. Descriptive statistics will be calculated for the observed values as well as the change from Baseline values.

A table of treatment-emergent markedly abnormal results of ECG and ECHO that occur after Baseline as defined in Appendix Table 5 will be generated overall and by age cohort. The number and percentage of patients experiencing the abnormality as well as the total number of abnormalities will be presented. All ECGs and ECHOs with an abnormality will be listed.

## 6.10. Pharmacokinetic Analyses

For only Study 4658-102, results of all PK analyses will be provided as a separate PK report which will be appended to the final clinical study report (CSR) and summarized in the CSR.

Pharmacokinetic parameters of eteplirsen will be determined from plasma and urine concentration data. Individual plasma and urine levels of eteplirsen will be listed with the corresponding time relative to eteplirsen administration, and summary statistics will be generated by per-protocol time of collection. PK parameters for eteplirsen will be calculated using non-compartmental analysis and/or using population PK methodology, as appropriate. Actual sampling times will be used in all final PK analyses; per-protocol times will be used to calculate mean plasma concentrations for graphical displays.

Plasma and urine concentrations will be listed. PK parameters in plasma and urine will be summarized by dose level and age cohort. Plasma concentrations will be plotted versus elapsed time for dose level means and for individual patients. Dose proportionality will be evaluated across the range of doses studied.

## 7. CHANGES IN PLANNED ANALYSES

## 7.1. Changes from Clinical Protocol-Planned Analyses

Compared to the clinical protocol of 4658-102 (Version 4, dated 07 February 2020) the interim analysis 4658-102 is removed. There are no other changes in this SAP.

## 7.2. Changes from Previous Statistical Analysis Plans

Not applicable.

## 8. APPENDIX

## 8.1. Criteria of Abnormalities

		Predefined Change		Markedly Abnormal	
Test	Unit	Decrease	Increase	Criteria	
BUN	mmol/L	NA	NA	Value > 1.5× Baseline and > ULN	
Creatinine	µmol/L	NA	35	Value > ULN	
Sodium	mmol/L	8	8	NA	
Potassium	mmol/L	1.1	1.0	Value > 5.5 mmol/L or < 3 mmol/L	
Chloride	mmol/L	9	8	NA	
Uric acid	µmol/L	NA	NA	> ULN	
Calcium a	mmol/L	0.30	0.30	NA	
AST (SGOT)	U/L	NA	NA	Value $\geq 2 \times$ Baseline Value	
ALT (SGPT)	U/L	NA	NA	Value $\geq 2 \times$ Baseline Value	
Gamma Glutamyl Transferase	U/L	NA	NA	Value > 3× Baseline or > ULN	
Alkaline phosphatase	U/L	NA	NA	Value > 1.5× ULN	
Albumin	g/dL	1	1	< LLN or > ULN	
Total bilirubin b	µmol/L	NA	10	Value > 1.5× ULN	
Creatine phosphokinase	U/L	NA	NA	Value $\geq 2 \times$ Baseline Value	
Cystatin C	mg/L	NA	NA	> ULN	

## 8.1.2 Appendix Table 2. Hematology Laboratory Abnormalities of Interest

LLN = lower limit of normal; ULN = upper limit of normal

#### 8.1.3 Appendix Table 3. Urinalysis Laboratory Abnormalities of Interest

Test	Markedly Abnormal Criteria	
Protein in urine	> 1+	
Blood in urine	Positive (+)	
RBC in urine	> 0	

#### 8.1.4 Appendix Table 4. Vital Sign Abnormalities of Interest

Variable	Units	Markedly Abnormal Criteria Lower limit	Markedly Abnormal Criteria Upper limit
Systolic blood pressure	mmHg	< 90	> 140
Diastolic blood pressure	mmHg	< 40	> 90
Pulse Rate	beats/minute	< 60	> 130
Respiratory Rate	Breaths/min	< 12	> 20
Temperature	°C	< 36.0	> 38.0
Weight	kg	Decrease of 7% or more from Baseline	

Variable	Units	LLN	ULN	Age Group (years)	Markedly Abnormal Criteria
Heart Rate	beats/min	60	130		NA
QTcF Interval	msec	NA	NA	< 12	> 480
				All	< 320
					Increase > 60
					> 450
					> 480
					> 500
QRS Interval	msec	NA	NA	< 12	Intraventricular conduction delay (IVCD) or any QRS conduction disturbance with a QRS > 110 msec
PR Interval	msec	NA	NA	< 12	> 190
LVEF	%	NA	NA	All	< 55%
Fractional Shortening	%	NA	NA	All	< 29%

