9.2. Treatments Administered

Eligible patients will receive a once weekly IV infusion of eteplirsen for up to 96 weeks. Eteplirsen should be prepared for dosing by following the steps detailed in the study-specific Pharmacy Manual.

The starting dose is 2 mg/kg eteplirsen, with escalation to 4, 10, 20, and 30 mg/kg over the course of the dose-titration period.

The following guidelines for the timing of dosing should be followed throughout the study:

- Patients should receive Eteplirsen once every 7 days starting on Week 1. A window of ± 3 days from the scheduled dose is acceptable after the first infusion.
- Patients may not receive 2 separate doses of Eteplirsen within the same 60-hour period.
- The Medical Monitor should be contacted in the event of ≥2 consecutive missed doses.

The administered dose is calculated by patient weight, which will be collected on a weekly basis and used to calculate the dose to be administered at the next visit(s). For example, the weight collected at Week 2 will be used to calculate the doses to be infused during the Week 3 visit.

Eteplirsen should be diluted in a normal saline, where the final volume, after eteplirsen has been added, equals the volume appropriate for the patient's weight. The drug delivery bag, syringe or flask is to be labeled in accordance with standard pharmacy practice and to include total volume as well as drug dose in milligrams. Eteplirsen will be diluted in normal saline to a total volume per Table 5 and infused IV for approximately 35 to 60 minutes using an infusion or syringe

pump. It is recommended that a topical anesthetic cream be applied to the infusion site prior to each administration of eteplirsen.

Table 5: Example Eteplirsen Dilution Scheme

Patient Weight	Total Eteplirsen Dose (30 mg/kg)	Total Volume of Eteplirsen Drug Product	Dilution in Saline up to Total Volume of:	Maximum Eteplirsen Concentration in Infusion
<5 kg	<150 mg	<3 mL	10 mL	15 mg/mL
5 to 10 kg	150 to 300 mg	3 to 6 mL	15 mL	20 mg/mL
10 to 15 kg	300 to 450 mg	6 to 9 mL	25 mL	18 mg/mL
15 to 25 kg	450 to 750 mg	9 to 15 mL	50 mL	15 mg/mL
>25 kg	>750 mg	>15 mL	100 mL	

Note: Refer to the Pharmacy Manual for other dosing dilution schemes.

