10.3.3. Height/Length and Weight

Height/length and weight will be measured at the time points specified in Table 2 and Table 3 prior to study drug infusions, to determine the volume of study drug to be administered. Details about how weight measurements are obtained are provided in the Study Operations Manual. If a patient's weight or height/length varies by more than 10% from the prior visit, the patient should be re-weighed to confirm the result, and an explanation of the change should be documented.

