## **4. STUDY DESCRIPTION**

## 4.1. Study Overview

#### Study 4658-102

This is a multicenter, open-label, dose-escalation study to evaluate the safety, tolerability, PK, and efficacy of once-weekly IV infusions of eteplirsen in approximately 12 male patients, ages 6 months to 48 months (inclusive), who have genotypically confirmed DMD with a deletion mutation amenable to exon 51 skipping.

Patients will be evaluated for inclusion during the Screening Period of up to 2 weeks to assess eligibility. Written informed consent from the parent/legal guardian to participate in the study must be obtained prior to beginning any study-related procedures.

Patients will be enrolled into 1 of 2 age cohorts: Cohort 1 of approximately 6 male patients age 24 to 48 months and Cohort 2 of approximately 6 male patients age 6 months to <24 months.

After the first 3 patients in Cohort 1 have completed 12 weeks of eteplirsen therapy, including 2 infusions each at 2, 4, 10 and 20 mg/kg and 4 infusions at 30 mg/kg, the Data Monitoring Committee (DMC) will review the safety data and determine whether to begin enrollment of the younger patients (Cohort 2). The DMC will also review safety data at least weekly through the first 12 weeks of dosing for the first 3 patients of each age cohort. Reviews will be at least quarterly thereafter.

The dose-titration period will last 10 weeks overall (1 infusion/week) to slowly achieve the target dose of 30 mg/kg. Eteplirsen dosing will begin at 2 mg/kg for 2 weeks (Weeks 1 and 2) and will escalate to 4 mg/kg (Weeks 3 and 4), 10 mg/kg (Weeks 5 and 6), 20 mg/kg (Weeks 7 and 8), and 30 mg/kg (Weeks 9 and 10). Patients will continue to receive 30 mg/kg eteplirsen for the duration of the study. The duration of each patient's treatment in the study is expected to be at least 48 weeks (including the 10-week titration period), and patients may continue to receive treatment in the study for up to 96 weeks. Study drug may be interrupted or discontinued for specific safety reasons.

Safety will be regularly assessed throughout the study via the collection of AEs, clinical safety laboratory test results (blood chemistry, hematology, coagulation, urinalysis), ECGs, ECHOs, vital signs, and physical examinations.

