## 5. GENERAL STATISTICAL METHODS AND CONVENTIONS

## 5.1. General Methods

Summary statistics will be presented by cohort, unless stated otherwise.

For continuous variables, descriptive statistics will include the number of patients with data to be summarized (n), mean, standard deviation (SD), median, minimum, and maximum.

For categorical/qualitative variables, descriptive statistics will include frequency counts and percentages. The total number of patients in the cohort will be used as the denominator for percentage calculations, unless stated otherwise.

Summaries will be for the following cohorts:

- Cohort 1 (age 24 to 48 months)
- Cohort 2 (age 6 to <24 months)

safety s	et for the final analysis of 4658-1	102.	All analyses will be displayed on the
5.2.	Handling of Missing Data	a	
5.2.1			

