#### **Baseline Visit**

Baseline visit in Study 4658-102 will be considered the last visit prior to the initiation of eteplirsen in Study 4658-102.

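### The SAP's only weight criterion is tied to pre-dose weight in growing children, so the fall needed to trigger it rises above the nominal 7% as they grow

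*SAP*

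**What the plan says.** SAP Appendix Table 4 (8.1.4) gives weight a single markedly abnormal criterion, "Decrease of 7% or more from Baseline". It has no upper limit, and no criterion uses a previous weight, a highest weight or age. The reference does not move: "Baseline visit in Study 4658-102 will be considered the last visit prior to the initiation of eteplirsen" (SAP 5.7).

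SAP 6.8.7 uses the appendix in two ways. It feeds a table of treatment-emergent markedly abnormal results, overall and by age cohort, and a listing: "All vital sign values with an abnormality of interest will be listed". The same section summarizes the largest absolute change from Baseline.

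Cohort 1 enters at 24 to 48 months and Cohort 2 at 6 to under 24 months (SAP 5.1). Treatment is expected to last at least 48 weeks, and "patients may continue to receive treatment in the study for up to 96 weeks" (SAP 4.1).

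On the protocol side, the dose is "calculated by patient weight, which will be collected on a weekly basis" (9.2). Section 10.3.3 has a visit-to-visit check, which opens "If a patient's weight or height/length varies by more than 10% from the prior visit" and requires re-weighing and a documented explanation. Section 13.8.2.2 plans by-visit summaries of weight and of its change from baseline.

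**The concern.** A fixed percentage below Baseline suits patients whose weight is roughly stable. Here the patients are infants and young children followed for one to two years. As a child grows, current weight moves away from the flag line, and the loss needed to reach the line grows with it. The label still says 7%, but the effective threshold is higher for any child who has gained weight, and it is highest for those who have grown most in proportion, generally the youngest.

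Worsening of vital signs is part of the primary safety endpoint, and the SAP places weight in its vital-sign abnormality table. A low or zero count in the weight row could be read as absence of marked weight loss when, late in treatment, the rule could show only a much larger loss than its label states. The same count would also carry a different meaning in each cohort column.

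**Working it through.** The plan states no growth figure and no operating characteristic for this criterion, so there is no figure of its own to reproduce.

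**Inputs from the documents.** Flag line 0.93 × Baseline weight (SAP Appendix Table 4); Baseline fixed before the first dose (SAP 5.7); entry ages 6 to 48 months (SAP 5.1); treatment 48 to 96 weeks (SAP 4.1); weekly weights (protocol 9.2).

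**Step 1: the fall needed.** Let W0 be Baseline weight and (1+g)W0 the current weight. The flag fires at 0.93·W0, so the fall needed as a fraction of current weight is

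L = 1 - 0.93/(1+g).

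| Growth g since Baseline | Fall needed L |
|---|---|
| 0% | 7.0% |
| 5% | 11.4% |
| 10% | 15.5% |
| 20% | 22.5% |
| 24% | 25.0% |
| 30% | 28.5% |
| 50% | 38.0% |

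This step is exact and needs no growth assumption. Conversely, L = 25% requires g = 0.93/0.75 - 1 = 24%.

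**Step 2: timing, under assumed growth.** The entry weights and yearly gains below are assumptions given as ranges, not figures from the documents. Gains accrue linearly within each year of 52.18 weeks. Worked examples at week 48, slow growth:

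- Entry at 6 months: gain 2.4 × 48/52.18 = 2.21 kg; g = 2.21/8.0 = 0.276; L = 1 - 0.93/1.276 = 27.1%.
- Entry at 48 months: gain 1.7 × 48/52.18 = 1.56 kg; g = 1.56/16.3 = 0.096; L = 1 - 0.93/1.096 = 15.1%.

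| Entry age | Assumed entry weight | Assumed gain per year (year 1; year 2) | L, week 12 | L, week 24 | L, week 48 | L, week 96 | Week when g = 24% |
|---|---|---|---|---|---|---|---|
| 6 months | 8.0 kg | 2.4–3.2; 2.0–2.6 kg | 13.0–14.8% | 18.3–21.5% | 27.1–32.0% | 38.4–44.4% | 31–42 |
| 12 months | 9.6 kg | 2.0–2.7; 1.8–2.4 kg | 11.3–12.6% | 15.1–17.7% | 22.0–26.1% | 31.9–37.6% | 45–61 |
| 24 months | 12.2 kg | 1.7–2.4; same | 9.9–11.0% | 12.6–14.7% | 17.6–21.3% | 26.0–31.7% | 64–90 |
| 48 months | 16.3 kg | 1.7–2.4; same | 9.2–10.0% | 11.3–12.9% | 15.1–18.1% | 22.0–26.8% | 85, or not by 96 |

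**Step 3: does the re-weigh check cover the gap?** It acts on changes above 10% between visits. A loss of one quarter can pass it if spread over ln(0.75)/ln(0.90) = 2.7, that is, three weekly visits. Three falls of 10% each give 1 - 0.90³ = 27.1%, and none exceeds 10%.

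**Step 4: after the change.** Measured from the highest previous on-study weight, the flag line is 0.93 × that weight, so a child at his highest weight needs a 7% fall whatever g is.

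**The case against.** The strongest reply is that this is one descriptive row in a single-arm study of about 12 patients, and that weight is visible elsewhere. All safety data are listed (SAP 6.8), so individual trajectories can be read. Weight and its change from baseline are summarized by visit. Clinically significant examination findings are recorded as adverse events, the DMC reviews safety data throughout, and an abrupt change of more than 10% triggers re-weighing. Protocol 10.3.2 does not count weight among the vital signs, and no decision rule depends on the row.

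Much of that stands. It limits the consequence but does not repair the criterion. The re-weigh check is a site measurement check that feeds no SAP table and can miss gradual loss. The largest absolute change from Baseline will usually be a gain in a growing child. By-visit means can hide one child's loss behind the growth of the others.

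A reader might infer stronger conclusions that the documents do not support:

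- *A child could lose a quarter of body weight unflagged after the first few months.* That needs 24% growth. Under the assumed rates it comes at about weeks 31 to 42 for entry at 6 months, and at about week 85 or not within 96 weeks for entry at 48 months. At week 12 the fall needed is about 9 to 15%.
- *Such a loss would go unseen.* Only the SAP abnormality table, and the listing built on the same criteria, would miss it.
- *The row will read zero.* No data support that prediction, and early in treatment the rule works near its nominal 7%.
- *The cohort comparison is biased.* No formal comparison is planned; the results are descriptive and shown side by side.

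**Conclusion.** The criterion does not keep its stated meaning in this population. The formula is exact, and any weight gain pushes the effective threshold above 7%. The timing rests on assumed growth, because the documents give none. On those assumptions the fall needed at week 48 is roughly two to four and a half times the nominal value (15.1/7 = 2.2 to 32.0/7 = 4.6). Sensitivity declines through treatment and varies with entry age as a gradient: a child entering Cohort 2 at just under 24 months would behave much like the youngest entrants to Cohort 1. The criterion should be changed because the row contributes to safety reporting on the primary endpoint and the correction is cheap. It does not threaten the overall safety evaluation, since the underlying weights are reported elsewhere.

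**What to change.** Replace the weight row in SAP Appendix Table 4 with: *weight at least 7% below the highest previous on-study weight (Baseline included), confirmed at the next scheduled weight*. State how a fall at the last available weight is handled, since it cannot be confirmed; listing it separately as unconfirmed would suffice.

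Optionally, add change from Baseline in weight-for-age z-score to the weight summary, so that failure to gain is also visible. The SAP would have to name the growth reference, because neither document supplies one.

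The cost is SAP wording and minor programming on weekly weights already collected, with no new trial data. The downside is some extra flags from weighing error or short illness, because a running maximum over many weekly weights tends to pick up high readings; 7% of 8 kg is only 0.56 kg. The confirmation step limits this. The change affects how weights are reported, not how patients are managed.
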